5.1 Agent Administration

SYLATRON will be administered as a weekly subcutaneous injection for up to 18 courses with 6 injections per course. Six consecutive weeks will constitute one course and subsequent courses will immediately follow, with no break in the administration of the drug. All patients will receive a dose of 1 mcg/kg/week. The patient's actual weight (in kilograms) should be used when calculating the dose of SYLATRON and doses should be re-adjusted if necessary at the time of each clinic evaluation. See Appendix C for the SYLATRON dosage calculation and dosage chart. Patients or parents will be taught to administer the medication in the outpatient setting (see Appendix B for a parent handout on administering subcutaneous injections). Patients or their guardians will keep a diary to document SYLATRON administration (available on the PBTC-039 webpage).

Since constitutional symptoms (e.g., fatigue, myalgias, fever) are generally the most severe after the first few doses, acetaminophen (15 mg/kg up to max dose of 1000 mg) should be given 30 minutes prior to administering the first six doses (first course) of SYLATRON and prior to subsequent doses if needed. For fever that develops after a dose of SYLATRON, Acetaminophen (15 mg/kg up to max dose of 650 mg PO) can be given q 4-6 hours as needed, but should not exceed 75 mg/kg/day for a total dose of up to 3000 mg/day. Acetaminophen can also be alternated with ibuprofen (10 mg/kg up to a max dose of 600 mg) every 6-8 hours as needed. Patients who are on replacement steroids for adrenal insufficiency should receive stress dose steroids for any fever > 101 degrees Fahrenheit (38.3 degrees Centigrade). Please see Appendix D for suggested stress steroid dosing for SYLATRON related fever.

It is recommended that a follow-up call be placed to the patient or parent within 72 hours of the first dose to evaluate for toxicities and review optimal management.

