5.4 Off Treatment Duration of Follow Up

Patients who are off protocol therapy must be followed until an "Off Study Criterion" is met (see section 5.6).

- 5.4.1 Patients who have had progression/recurrence will be followed for 30 days after the last dose of SYLATRON or until the resolution of all SYLATRON related toxicities, whichever is longer.
- 5.4.2 Patients who discontinue for reasons other than progression/recurrence of disease should continue to be followed for progression/recurrence, i.e. until they meet the Off Study criteria (below). Follow-up data will be required.
- 5.4.3 Patients removed from study for unacceptable adverse event(s) will be followed until resolution or stabilization of the adverse event and they meet one of the Off Study criteria (below).

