9.3.3 Timing of Assessment

Imaging studies will be done at baseline prior to PEGINTERFERON ALFA-2B therapy and every 12 weeks for the first 9 courses (approximately 1 year) then every 18 weeks thereafter until subjects develop evidence of disease progression, unacceptable toxicity or completion of 18 courses (approximately 2 years) of PEGINTERFERON ALFA-2B therapy.

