10 STUDY CALENDAR

Table 2 Standard Clinical and Laboratory Assessments

| | Pre- Therapy | Course 1 | Course 2-9 | Course 10-18 | End of Treatment |
|--|---------------------------|----------------|----------------|---------------------------|---------------------|
| PHYSICAL ASSESSMENTS | | | | | |
| Complete History | X | | | | |
| Interval History | | X ^A | X ^C | $\mathbf{X}^{\mathbf{F}}$ | X |
| Psychiatric History** | X | X ^A | XC | $\mathbf{X}^{\mathbf{F}}$ | X |
| Performance status | X | X ^A | X ^C | $\mathbf{X}^{\mathbf{F}}$ | X |
| Physical including neurologic exam | X | X ^A | X ^C | $\mathbf{X}^{\mathbf{F}}$ | X |
| Visual field evaluation (as feasible) | X | | X ^C | $\mathbf{X}^{\mathbf{F}}$ | |
| Ophthalmology evaluation | X | | X ^C | $\mathbf{X}^{\mathbf{F}}$ | |
| Vital signs | X | X ^A | X ^C | $\mathbf{X}^{\mathbf{F}}$ | X |
| LABORATORY EVALUATION | | | | | |
| CBC (WBC, Hgb, Hct, Platelets, ANC, ALC) | X | X ^A | XC | \mathbf{X}^{F} | X |
| Serum Chemistries (Electrolytes, BUN, Creatinine, SGOT(AST), SGPT(ALT), Total Bilirubin, TSH | X | X ^A | X ^C | X ^F | X |
| Urinalysis for protein (Urine Dip) | X | X ^A | X ^C | X ^F | X |
| Serum or urine pregnancy test (for females of childbearing potential) | X | X ^C | X ^C | X ^F | |
| IMAGING EVALUATION | | | | | |
| Brain MRI with thin cuts through the sella ^D | X | | X^B | $\mathbf{X}^{\mathbf{G}}$ | X |
| OTHER | | | | | |
| Biology Studies (assessment of WNT and MAPK pathway activation) | $\mathbf{X}^{\mathbf{E}}$ | | | | |
| FFPE tumor tissue for PBTC CRB | X^{E} | | | | |
| PBMC for PBTC CRB | X^{E} | | | | |

- Assessments should be done prior to starting course 2, i.e. prior to the 7th injection.
- B Obtain every 12 weeks at time of visit and at time of progression as feasible
- C Obtain every 12 weeks at time of visit
- D See section 9.3 9.3.1
- E See section 9.1.
- F Obtain every 18 weeks at time of visit
- Obtain every 18 weeks at time of visit and at time of progression as feasible

^{*} NOTE: Patients who do not have a Brain MRI performed at or after 9 courses (approximately 12 months) will be considered failures for the purpose of assessing the primary objective according to the statistical design. See section 13.4.1.

** Psychiatric History: patient/family will be queried about mood, depression and suicidal ideations at each study visit. If there are any concerns about significant depression or any suicidal ideation, patient should be referred to Psychiatrist.

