Kaplan-Meier estimates of distributions of PFS for all eligible patients who receive at least one dose of PI will be provided separately for each stratum. PFS will be measured from the date of initial treatment to the earliest date of disease progression, second malignancy or death for any reason for patients who fail; and to the date of last contact for patients who remain at risk for failure.

Both for objective response assessments as well as PFS calculations, the assessments made at the treating site will be used. Any discrepancies between the treating sites' assessments and the central review will be recorded and described.

Toxicity data will be summarized via frequency tables both for episodes and for number of patients separately for each stratum. We will also tabulate the data related to dose reductions and treatment discontinuation due to toxicity.

Analysis Plan for Central Imaging Review:

All imaging studies obtained during the first year of treatment in Stratum I as well as all scans with the smallest disease measurement recorded since the start of protocol and scans documenting objective response or progressive disease in both strata will be centrally reviewed at the end of the study. We will summarize any discordance between site's assessment and the central review across patients within a stratum as well as on a per patient basis taking into account the longitudinal data that will be available especially in Stratum I. Specific attention will

be given to PD assessment as we anticipate that there will be cases where PD criteria will be satisfied based on protocol definition but not by MacDonald criteria and vice-versa.

Analysis Plan for the WNT pathway activation data:

We will summarize the frequency of nuclear beta-catenin by IHC in FFPE tumor sections. We will also explore associations between presence of nuclear beta-catenin and outcome. Separately in each stratum, if we observe 10 or more responses among patients from whom biology data are available, we will use exploratory logistic regression models to look for associations between biological markers and response. Similarly, if we observe 10 or more progressions among patients from whom biology data are available in a stratum, we will explore associations between biological markers and PFS. Otherwise association with response and PFS will be summarized descriptively.

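### PFS is censored at last contact, but no MRI is scheduled after treatment ends, so contact without a scan counts as progression-free time and PFS can be overstated

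*Combined protocol and SAP*

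**What the plan says.** The PFS rule is in the Analysis Plan of section 13.3: "PFS will be measured from the date of initial treatment to the earliest date of disease progression, second malignancy or death for any reason". Patients without an event are followed "to the date of last contact for patients who remain at risk for failure". Last contact is not defined and is not tied to a disease assessment.

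Section 9.3.3 sets MRI every 12 weeks for the first 9 courses, "then every 18 weeks thereafter until subjects develop evidence of disease progression, unacceptable toxicity or completion of 18 courses". The study calendar (section 10) agrees. Its rule for courses 10 to 18 is "Obtain every 18 weeks at time of visit and at time of progression as feasible". It adds an end-of-treatment MRI and has no later column.

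Section 5.4.2 covers patients who stop for reasons other than progression. They "should continue to be followed for progression/recurrence, i.e. until they meet the Off Study criteria (below). Follow-up data will be required". It names no scan and no interval.

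Section 5.5 takes a patient off study on starting another therapy or on completing all specified evaluations and follow-up. Section 5.5.1 ends the collection of disease status at that date.

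**The concern.** Progression in section 11.1.3 is mostly an MRI finding: growth in the product of diameters plus growth in two dimensions, or a clinical deficit together with a smaller tumor change. A phone call or a visit without imaging cannot rule that out, yet it moves the censoring date forward. Such a patient stays in the Kaplan-Meier risk set with little chance of a recorded event, which lifts the curve.

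The plan is stricter elsewhere. For the primary endpoints, patients who are not evaluated count as failures (section 13.4.1 and the calendar note). In the cumulative-incidence analysis of response, removal for toxicity is a competing event, and stable patients are censored at last treatment. Only PFS credits unassessed time. Take a Stratum 1 patient who stops for toxicity at month 4, is never scanned again and is phoned at month 13. That patient is a failure for the primary endpoint and progression-free at one year in the PFS curve.

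At stake is the PFS estimate by stratum (objective 1.2.2), which readers may set beside other series.

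**Working it through.** The plan gives no expected PFS value or PFS sample size, so there is no stated PFS figure to reproduce. The treatment length can be checked: "for up to 18 courses with 6 injections per course", at 6 weeks per course, is 18 × 6 = 108 weeks, or 108 / 4.345 = 24.9 months. That agrees with the plan's figure of about 2 years.

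**Inputs from the documents.** MRI at weeks 12, 24, 36 and 48, then every 18 weeks (66, 84, 102). The 75% is the Stratum 1 target for 1-year stabilization, borrowed here as the true 1-year PFS.

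**Assumptions not in the documents.** Exponential progression. A share p of patients (10%, 20%, 30%) stops drug, uniformly over weeks 0 to 52, and has no scheduled MRI afterwards. All remain in contact to week 104. A share q of off-treatment progressions is still found, on the date when a scheduled scan would have shown them. The 18-week interval is counted from week 48.

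**Step 1, full scanning.** S(t) = 0.75^(t/52), with events dated at the next scan. At week 102, S = 0.75^(102/52) = 0.569. At week 54 the last scan is week 48, so the curve reads S(48) = 0.767.

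**Step 2, stoppers with nothing found later.** Their only recorded events are those seen by the last scan before stopping. The share without a recorded event is

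(12/52) × (1 + 0.936 + 0.876 + 0.819) + (4/52) × 0.767 = 0.838 + 0.059 = 0.897.

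**Step 3, last-contact censoring.** Nobody is censored before week 102, so the Kaplan-Meier value is the proportion without a recorded event:

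(1 − p) × 0.569 + p × [(1 − q) × 0.897 + q × 0.569] = 0.569 + p × (1 − q) × 0.328.

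| Share stopping | None found | Half found | All found |
|---|---|---|---|
| 10% | 0.60 | 0.58–0.59 | 0.57 |
| 20% | 0.63 | 0.60 | 0.57 |
| 30% | 0.67 | 0.62 | 0.57 |

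Simulation with 200,000 patients agrees (none found: 0.602, 0.635, 0.666; half found: 0.583, 0.603, 0.619). At week 54 the excess with none found is p × (0.897 − 0.767) = p × 0.130, which is 1 to 4 points.

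**Step 4, adding the end-of-treatment scan.** The 0.897 becomes the average of S at the stopping date, 0.25 / 0.2877 = 0.869. Week 102 with none found is then 0.60, 0.63 and 0.66, so little changes.

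**Step 5, another progression rate.** The earlier interferon alfa-2a study cited in section 2.2.1 had a median time to progression of 25 months. A simulation used that median, last contact uniform over 24 to 60 months, and toxicity stops of 10% or 30% by month 12. At 24.9 months the excess ran from about 0.02 (10% stopping, half found: 0.526 against 0.502) to 0.13 (30%, none found: 0.635 against 0.505). It was zero when all were found. With no early stops, so that only course-18 completers were affected, there was no difference through 24.9 months. At 36 months PFS read 0.50 (none found) or 0.45 (half found) against 0.40.

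**Step 6, the replacement rule.** In the set-up of steps 1 to 3, censoring at the last scan returns 0.57 in every scenario with none found. With 30% stopping and off-treatment progressions found only through symptoms, it falls to 0.53 (half found) or 0.49 (all found). If the same patients are scanned whether or not they progress, it returns 0.57 throughout.

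**The case against.** A reader might infer that PFS is overstated as a matter of fact. The documents do not support that. Section 5.4.2 requires follow-up for progression and data from it, and step 3 gives no bias if that follow-up finds every progression. What is missing is the assessment it relies on, not the follow-up itself.

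A reader might also infer that progression cannot be detected without a scan. That is too strong. Section 11.1.3 has clinical routes, such as cyst aspiration for symptom control in Stratum 1 after 12 months, or repeated aspirations in Stratum 2 after 12 months. Death and second malignancy need no MRI. Still, most deficit-based progression also needs a tumor change.

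Contact is bounded too. Sections 5.5 and 5.5.1 end data collection at new therapy or completed follow-up, so contact to week 104 for every stopper is an upper-end assumption. The form that sets data timing is not among the documents and may specify follow-up assessments.

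The most substantial objection concerns the remedy: last-scan censoring can turn the bias downward, as step 6 shows. It does so when off-treatment events are counted while event-free stoppers have no later assessment. That calls for a safeguard but does not rescue last-contact censoring, which is right only if off-treatment progressions are essentially all found.

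Finally, PFS is secondary and descriptive, with no test or decision rule. That stands and limits the weight of the point.

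**Conclusion.** The point holds in conditional form: the stated rule credits unscanned time as progression-free, so PFS can be overstated. Under the assumed inputs the week-102 excess is 3 to 10 points if no off-treatment progression is found, about 2 to 5 points if half are found, and zero if all are found. For scale, the standard error of a proportion of 0.57 in 28 patients is √(0.57 × 0.43 / 28) = 0.094, so the worst case is about one standard error.

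The stop shares, the length of contact and the share found are assumptions; the documents give none of them. Bias in the first two years comes from early stops alone. Course-18 completion affects only the curve beyond about 25 months. The primary endpoints, and the go/no-go decisions that rest on them, are unaffected. This is a cheap improvement to a secondary endpoint.

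**What to change.** Replace the censoring clause in section 13.3 along these lines: patients without an event are censored at their last disease assessment adequate to show no progression (MRI on or off treatment); deaths and second malignancies still count on their dates. State that a patient with no assessment after baseline is censored at first dose.

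Keep last-contact censoring as a sensitivity analysis, because the two rules can err in opposite directions when off-treatment progressions are found through symptoms. Report by stratum how many patients have contact beyond their last scan and for how long. If few do, the choice hardly matters.

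Reconcile section 5.4.2, section 9.3.3 and the calendar on which disease assessment off-treatment follow-up relies on; that is for the sponsor to settle. At the same time, correct the pointer in section 5.4, which sends the reader to section 5.6 for off-study criteria that stand in section 5.5.

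Cost: one sentence for the rule, a short clarification of follow-up, and capture of off-treatment scan dates, which the documents do not show to be collected. Reported follow-up will be shorter and intervals slightly wider. Making the change before the analysis avoids choosing a rule after seeing the curves.

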2.5 Rationale for Correlative Studies

2.5.1 WNT and MAPK pathway activation

Recent genomic studies have demonstrated that each of the two histologic subtypes of craniopharyngioma (adamantinomatous and papillary) is characterized by the presence of a specific genetic alteration.²⁸ Adamantinomatous craniopharyngiomas, which are most common in children, exhibit near-universal mutation of beta-catenin (*CTNNB1*), confirming recent evidence that craniopharyngiomas arise from activation of beta-catenin (a Wnt pathway gene) in pituitary progenitors during embryogenesis²⁹. Of note, craniopharyngiomas with mutations in *CTNNB1* can be reliably identified by detection of nuclear immunoreactivity for the beta-catenin protein, which is the most commonly-used clinical test for alterations in this gene. These results confirmed an earlier study where all 10 cases of adamantinomatous craniopharyngioma harbored beta-catenin mutations and stained for nuclear expression of beta-catenin.³⁰ Papillary

craniopharyngiomas, in contrast, are characterized by frequent *BRAF* V600E mutations, indicating activation of the MAPK signaling pathway.²⁸ Although in general mutations in *CTNNB1* and *BRAF* are mutually-exclusive in craniopharyngiomas, cases have been identified in which both genes are mutated in the same tumor.³¹ We propose to validate these observations using immunohistochemistry for nuclear beta-catenin and pyrosequencing for detection of *BRAF* V600E in FFPE sections in this pediatric series of craniopharyngiomas.

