9.1.5 Assessment of WNT and MAPK Pathway Activation

FFPE tissue is obtained for diagnostic purposes in virtually all brain tumor resections, unlike frozen tumor material, which is obtained at the discretion of the neurosurgeon. Tumor material submission is optional but strongly encouraged for exploration for evidence of WNT pathway activation by immunohistochemistry (IHC) for nuclear beta-catenin protein and MAPK pathway activation by pyrosequencing for BRAF V600E mutation in tumor tissue. Investigators should make every effort possible to obtain tissue when available and must review with the study chair or co-chair if tissue is not available.

• WNT Pathway Activation IHC:

FFPE tumor sections will be evaluated for evidence of WNT pathway activation through staining for nuclear and cytoplasmic beta-catenin expression (phospho- β catenin, β -catenin supplied by New England Biolabs, Beverly, MA). The assays have been developed and validated previously on medulloblastoma samples. ³³

• Detection of BRAF V600E mutation by pyrosequencing

FFPE tumor sections will be evaluated for evidence of MAPK pathway activation through detection of the BRAF V600E mutation by pyrosequencing, using protocols currently in use in the Molecular Neuropathology laboratory, Department of Pathology, Texas Children's Hospital.

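### The trigger for the marker models counts events only; it should also require a minimum number of patients in the smaller marker group and name a method for sparse data.

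*Combined protocol and SAP*

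**What the plan says.** Section 13.3, under the analysis plan for the WNT pathway activation data, first promises a summary of how often nuclear beta-catenin is found, and then: "We will also explore associations between presence of nuclear beta-catenin and outcome". The modelling rule applies to the strata one at a time: "if we observe 10 or more responses among patients from whom biology data are available, we will use exploratory logistic regression models". The stated purpose of these models is "to look for associations between biological markers and response". Ten progressions among patients with biology data open the corresponding exploration of PFS, for which no model is named. If the count is not reached: "Otherwise association with response and PFS will be summarized descriptively".

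The section sets no minimum for either marker category and does not say what to do if the data separate.

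Section 2.5.1 gives the background on the marker: "Adamantinomatous craniopharyngiomas, which are most common in children, exhibit near-universal mutation of beta-catenin". It adds that nuclear staining identifies these mutations reliably, and cites a series in which "all 10 cases of adamantinomatous craniopharyngioma harbored beta-catenin mutations and stained for nuclear expression of beta-catenin". BRAF V600E is described as frequent in the papillary subtype. The section also says that the trial is to validate these observations. Section 9.1.5 makes tissue voluntary: "Tumor material submission is optional but strongly encouraged".

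**The concern.** A 10-event threshold is a guard against sparse data, but it protects only one margin of the table. With a present/absent marker, the odds ratio or hazard ratio also depends on how many patients are in the smaller marker group and whether events and non-events both occur there. If every patient is marker-positive there is no contrast to estimate. If the one or two marker-negative patients all share the same outcome, the maximum-likelihood estimate runs to zero or infinity.

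The plan's background makes such a split plausible. Yet once 10 events are seen, the rule sends the data to a model, and the descriptive fallback is no longer called for. What is at stake is the readability of objective 1.2.5: an unstable or infinite estimate, resting on one or two children, could be reported as an association.

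**Working it through.** **Plan figures.** The plan gives no power, precision or derivation for the marker models or for the threshold of 10. What can be checked is the designs that fix the stratum sizes.
- Stratum 1 (stop at 6 or fewer of 12; success at 18 or more of 28), by exact two-stage binomial: power 0.9017 against 0.902 stated. The attained level is 0.0815 against 0.082, and early stopping 61.3% and 5.4% against 61.6% and 5.0%. These small differences do not bear on this point.
- Stratum 2 (11 then 19): early stopping 69.7% and 6.1%, against 70% and 6% stated.

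So n = 28 and n = 19 are used as the maximum group sizes.

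**Inputs that must be assumed.** Marker prevalence q = 85%, 90% or 95%; tissue from every patient unless stated; no association between marker and outcome.

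**Step 1: expected marker-negatives, n(1 − q).** At 95%: 28 × 0.05 = 1.4 and 19 × 0.05 = 0.95. At 90%: 2.8 and 1.9. At 85%: 4.2 and 2.85.

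**Step 2: chance of no finite odds ratio with 10 responders.** Let m be the number of marker-negatives, binomial(n, 1 − q). If m = 0, the marker is constant. For small m ≥ 1 there is a zero cell when all negatives are non-responders or all are responders, with probability [C(n−10, m) + C(10, m)] / C(n, m).

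Worked case, n = 28, q = 95%:

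| m | P(m) | P(no finite OR given m) | product |
|---|---|---|---|
| 0 | 0.2378 | 1 | 0.2378 |
| 1 | 0.3505 | 1 | 0.3505 |
| 2 | 0.2490 | 0.5238 | 0.1304 |
| 3 | 0.1136 | 0.2857 | 0.0325 |
| 4 | 0.0374 | 0.1598 | 0.0060 |
| 5 | 0.0094 | 0.0897 | 0.0008 |

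The sum is 0.758. All cases:

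| Prevalence | n = 28 | n = 19 |
|---|---|---|
| 85% | 24% | 38% |
| 90% | 45% | 60% |
| 95% | 76% | 85% |

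**Step 3: how often the response trigger is reached, P(X ≥ 10), full tissue.** Stratum 2 at its 35% design rate: 8.75%; at 25%: 0.9%. Stratum 1 has no design response rate. The earlier interferon study in section 2.2.1 had 1 CR, 1 PR and 1 minor response in 12, so 2/12 = 17% or 3/12 = 25%. At those rates the chance is 1.4% and 14%.

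**Step 4: how often the progression trigger is reached in Stratum 1.** Assume all 28 enrol, one-year stabilization at the 75% target, and a constant hazard over about two years: 1 − 0.75² = 0.4375 progress, and P(X ≥ 10 of 28) = 85%. If half progress it is 96%. With tissue from 80%, 0.8 × 0.4375 = 0.35 and the chance is 54%.

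**Step 5: the same gap for PFS.** In 28 patients, the chance that the marker is constant or one marker group has no progression is 60% with 10 progressions and 49% with 14 at 95% prevalence. At 90% it is 35% and 23%.

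**The case against.** Several points on the other side stand.

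- **Prevalence is open.** A reader might infer that the plan itself says the marker will be nearly constant, so that the models cannot be estimated. The documents do not go that far. The near-universal figure belongs to the adamantinomatous subtype; any histologically verified craniopharyngioma up to age 25 is eligible, papillary tumours are not excluded, and the trial sets out to validate the observation. At 85% to 90% prevalence a finite estimate exists in about 40% to 76% of cases. This is a risk, not a certainty.
- **Other markers.** Section 13.3 speaks of markers in the plural, and section 9.1.5 also covers cytoplasmic and phospho-beta-catenin staining, for which no prevalence is given. Those may be better balanced.
- **Outcome classes.** It is tempting to say that the threshold counts the wrong class, because non-responders are the smaller group in Stratum 2 once 10 of 19 respond. At the threshold that is 9 against 10. In Stratum 1, non-responders are fewer in only 0.8% and 6% of triggered cases at response rates of 25% and 35%. This deserves no separate rule.
- **The response rule is seldom reached**, and missing tissue makes it rarer still, because it counts only patients with biology data. This answer does not carry over to the progression rule in Stratum 1.
- **The analysis is exploratory**, and a constant or separated marker would usually show itself during fitting. That limits the harm, but leaves the choice of remedy until after the data are seen.

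**Conclusion.** The gap is real and minor. Followed as written, the rule can send sparse data to an ordinary model when the fallback would serve better. The size depends on prevalence: with 10 responders, the chance of no finite odds ratio runs from 24% to 76% (n = 28) and from 38% to 85% (n = 19) over assumed prevalences of 85% to 95%, with no true association. The progression rule is where this is most likely to matter. The 85% chance of reaching it in Stratum 1 rests on full accrual, full tissue and a constant hazard at the 75% target.

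No go/no-go rule, primary estimate or safety decision uses these models; only exploratory secondary objective 1.2.5 is touched.

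**What to change.** Amend the WNT paragraph of section 13.3 by about two sentences. Keep the strata separate and keep the trigger of 10 responses or 10 progressions. Add that a model is fitted only if the smaller marker group also has a minimum number of patients with data, for example 5 (an illustrative figure with no source in the documents), and that fitting uses Firth-penalized or exact methods. Otherwise report marker frequency with an exact interval and a descriptive cross-tabulation against outcome.

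Both parts are needed. With exactly 5 marker-negatives and 10 responders of 28, a zero cell still occurs with probability (8,568 + 252)/98,280 = 9%.

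Two further changes are not advised. Requiring 10 patients in the smaller outcome class would shut out Stratum 2 for good, since 10 + 10 = 20 exceeds 19. Pooling the strata would mix the different PD definitions of section 11.1.3, and at 95% prevalence all 47 patients give only an 8% chance of 5 or more negatives.

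The cost is that the models may often not be run. The chance of at least 5 marker-negatives at 85%, 90% and 95% prevalence is 41%, 14% and 1.2% for n = 28, and 14%, 3.5% and 0.2% for n = 19. The report would then be descriptive, which the plan already accepts as its fallback.
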